8.2 Regorafenib Dose Modifications

8.21 Regorafenib may be dose reduced per the table 8.21 in case of intolerable toxicity such as weight loss, fatigue, rash or anorexia.

Table 8.21 Recommended dose modification for toxicities except hand-foot-skin reaction, hypertension and ALT/AST/bilirubin			
NCI-CTCAE v5.0^a	Dose Delay	Dose Modification ^b	Dose for Subsequent Cycles
Grade 0-2	Treat on time	No change	
Grade 3	Delay until \leq Grade 2 ^c	Reduce by 1 dose level	If toxicity remains $<$ Grade 2, dose re-escalation can be considered at the discretion of the treating physician. If dose is re-escalated and toxicity (\geq Grade 3) recurs, institute permanent dose reduction.
Grade 4	Delay until \leq Grade 2 ^c	Reduce by 1 dose level. Permanent discontinuation can be considered at treating physician's discretion.	

^a NCI-CTCAE = National Cancer Institute - Common Terminology Criteria for Adverse Events, version 5.0
^b Excludes alopecia, non-refractory nausea/vomiting, lymphocyte count decreased, non-refractory hypersensitivity and nonclinical and asymptomatic laboratory abnormalities.
^c If no recovery after a 4 week delay*, treatment should be permanently discontinued unless subject is deriving clinical benefit.
* Modify according to study specific cycle length

If greater than 2 dose level reductions are required, regorafenib will be discontinued and the rest of the study follow up may be continued. The following tables outline dose adjustments for toxicities related to regorafenib except hand-foot skin reaction, hypertension and liver function test abnormalities.

The table above outlines dose adjustments for hematologic and non-hematologic toxicities related to regorafenib except PPES and hypertension. In addition to these recommended dose modifications, subjects who develop diarrhea, mucositis, anorexia or other events predisposing to fluid loss or inadequate fluid intake should be carefully monitored and rehydrated as clinically necessary. This is in order to minimize the risk of postural hypotension and renal failure.

8.22 Regorafenib may be dose reduced per Table 8.22b in case of Palmar-plantar erythrodysesthesia using Table 8.22a for grading guidelines.

Table 8.22a: Grading for Palmar-plantar erythrodysesthesia syndrome			
	Grade 1	Grade 2	Grade 3
NCI-CTCAE v5.0 Palmar-plantar erythrodysesthesia syndrome	Minimal skin changes or dermatitis (e.g., erythema, edema, or hyperkeratosis) without pain	Skin changes (e.g., peeling, blisters bleeding, edema, or hyperkeratosis) with pain	Severe skin changes (e.g., peeling, blisters, bleeding, edema, or hyperkeratosis) with pain

Further description / examples of skin changes	Numbness, dysesthesia / paresthesia tingling, painless swelling, or erythema of the hands and/or feet	Painful erythema and swelling of the hands and/or feet	Moist desquamation, ulceration, blistering, or severe pain of the hands and/or feet
Effect on activities	Does not disrupt normal activities	Limiting instrumental activities of daily life (e.g., preparing meals, shopping for groceries or clothes, using the telephone, managing money)	Limiting self-care activities of daily life (e.g., bathing, dressing and undressing, feeding self, using the toilet, taking medications) and not bedridden
a. Palmer-planter erythrodysesthesia syndrome is a disorder characterized by redness, marked discomfort, swelling, and tingling in the palms of hands or the soles of the feet.			

Table 8.22b Recommended dose modification for Palmar-plantar erythrodysesthesia syndrome reaction^a

Grade of event (NCI-CTCAE v5.0)	Occurrence	Suggested Dose Modification
Grade 1	Any	Maintain dose level and immediately institute supportive measures for symptomatic relief
Grade 2	1 st occurrence	Consider decreasing dose by one dose level and immediately institute supportive measures. If no improvement, interrupt therapy for a minimum of 7 days, until toxicity resolves to Grade 0-1 ^{b,d}
	No improvement within 7 days or 2 nd occurrence	Interrupt therapy until toxicity resolves to Grade 0-1. When resuming treatment, treat at reduced dose level ^b
	3 rd occurrence	Interrupt therapy until toxicity resolves to Grade 0-1. When resuming treatment, decrease dose by one dose level. ^{b,d}
	4 th occurrence	Discontinue therapy
Grade 3	1 st occurrence	Institute supportive measures immediately. Interrupt therapy for a minimum of 7 days until toxicity resolves to Grade 0-1. ^c When resuming treatment, decrease dose by one dose level. ^{b,d}
	2 nd occurrence	Institute supportive measures immediately. Interrupt therapy for a minimum of 7 days until toxicity resolves to Grade 0-1. ^c When resuming treatment, decrease dose by one additional dose level ^{b,d}
	3 rd occurrence	Discontinue treatment permanently.

a. More conservative management is allowed if judged medically appropriate by the treating physician.
 b. If toxicity returns to Grade 0-1 after dose reduction, dose re-escalation is not permitted.
 c. If there is no recovery after a 4-week delay, treatment with regorafenib will be discontinued permanently.
 d. Subjects requiring > 2 dose reductions should go off protocol therapy.
 e. The maximum daily dose is 160 mg.
 f. Refer to Section 9.0 for management strategies for Palmer-plantar erythrodysesthesia syndrome reactions.

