8.3 Criteria for discontinuing treatment with regorafenib

Treatment with regorafenib will be discontinued if any of the following criteria for discontinuation is met:

1. When regorafenib is considered to be ineffective
 - Radiographically confirmed disease progression.
 - Significant worsening of symptoms or physical findings (disease progression should be radiographically confirmed whenever possible).

2. When treatment with regorafenib cannot be continued
 - It is necessary to reduce the dose of regorafenib to less than dose level -2 according to the criteria for dose reduction/modification of treatment.
 - Treatment cannot be resumed within 28 days after modification of treatment due to an adverse event.
 - A 3rd episode of grade 3 hand-and-foot syndrome occurs despite symptomatic treatment and dose reduction of regorafenib.
 - Grade 4 hypertension.
 - Grade 4 or higher increase in AST/ALT, 2nd episode of grade 3 increase in AST/ALT or bilirubin > upper limit of normal x 2 and AST or ALT > upper limit of normal x 3.
 - Other grade 4 non-hematological toxicity.
 - The treating physician decides that treatment with regorafenib cannot be continued due to safety concerns.
3. Patient's request for discontinuation of treatment with regorafenib.
4. After enrollment, the patient is found to be ineligible for the study, and it is concluded that further treatment with regorafenib is detrimental to him/her.
5. Transfer to another institution for any reason during treatment with regorafenib.

8.4 Combination therapy of Anti-EGFR therapy (cetuximab (Cmab) OR panitumumab (Pmab)) and irinotecan

Treatment with cetuximab/panitumumab or irinotecan will be started if it is confirmed that all criteria for treatment are met prior to treatment initiation. If all criteria for starting treatment with Cmab/Pmab are met, but any of the criteria for starting treatment with irinotecan is not met, only Cmab/Pmab can be administered. If the case is reversed, however, irinotecan should not be administered alone (without Cmab/Pmab).

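### Table 8.22a makes painful, non-severe blistering Grade 2 by two of its rows and Grade 3 by the other, and the two grades lead to different regorafenib dosing at a first event

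*Combined protocol and SAP*

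**What the plan says.** Section 8.22 names Table 8.22a as the grading guide for this reaction and Table 8.22b as the source of the dose change. Table 8.22a describes each grade in three rows.

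- **CTCAE v5.0 row.** Grade 2 is "Skin changes (e.g., peeling, blisters bleeding, edema, or hyperkeratosis) with pain". Grade 3 is "Severe skin changes (e.g., peeling, blisters, bleeding, edema, or hyperkeratosis) with pain". The signs listed are essentially the same; the severity word separates the grades.
- **Further-description row.** Grade 2 is "Painful erythema and swelling of the hands and/or feet". Grade 3 is "Moist desquamation, ulceration, blistering, or severe pain of the hands and/or feet". Here the severity word attaches to pain only.
- **Activities row.** Grade 2 is "Limiting instrumental activities of daily life". Grade 3 is "Limiting self-care activities of daily life".

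Table 8.22b labels its grade column as the CTCAE v5.0 grade. For a first Grade 2 event it says "Consider decreasing dose by one dose level and immediately institute supportive measures", with interruption only if there is no improvement. For a first Grade 3 event it interrupts therapy for at least 7 days, until recovery to Grade 0-1, and resumes one dose level lower. Section 8.3 lists as a reason to stop regorafenib: "A 3rd episode of grade 3 hand-and-foot syndrome occurs despite symptomatic treatment and dose reduction of regorafenib".

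**The concern.** The rows of a grading table should lead to the same grade for the same patient. For one common-sense presentation these do not, and nothing says which row prevails. Two sites reading the table in good faith could therefore dose the same reaction differently.

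The timing adds weight. Section 1.4 puts this reaction in the first 1-2 weeks of regorafenib and names it among the toxicities that limit the drug's use. Section 8.0 requires the modification tables to be followed strictly in the first two cycles, so the conflict falls where sites have least latitude.

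A second consequence concerns the data. Sections 10.1, 10.52 and 16.326 grade and summarise adverse events by CTCAE v5.0. A site that doses from the further-description row and completes the adverse-event form from CTCAE would hold two grades for one event.

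**Working it through.** There is no figure in the plan to reproduce. The check sets the table cells side by side.

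**Step 1: grade one case.** Take painful blistering, not severe, limiting only instrumental activities.

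| Row of Table 8.22a | Feature that decides | Grade |
|---|---|---|
| CTCAE v5.0 | Blisters with pain, not severe | 2 |
| Further description | Blistering, no severity condition | 3 |
| Activities | Instrumental activities only | 2 |

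If the blistering is severe, the first two rows agree on Grade 3. The conflict between them is confined to painful blistering that is not severe.

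**Step 2: carry the grade into Table 8.22b.**

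| Occurrence | Read as Grade 2 | Read as Grade 3 |
|---|---|---|
| 1st | Continue; reduction considered; interrupt if no improvement | Interrupt at least 7 days; one level lower |
| 2nd | Interrupt; resume at reduced level | Interrupt at least 7 days; one further level lower |
| 3rd | Interrupt; one level lower | Stop permanently |
| 4th | Stop | Already stopped |

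Failure to improve within 7 days is handled like a 2nd Grade 2 occurrence. The sharp difference is therefore at a first event that improves.

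**Step 3: starting dose.** The levels in Table 8.1 are 80, 120 and 160 mg, so one level is 120 - 80 = 40 mg. Section 7.11 gives 80 mg in week 1 of cycle 1. One level below is 80 - 40 = 40 mg, which is not a listed level, and Section 8.12 takes patients needing less than 80 mg off treatment. For a first event at 80 mg, the Grade 3 reading therefore ends regorafenib, while the Grade 2 reading allows it to continue because the reduction is only to be considered.

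**Step 4: occurrence count.** Assume no escalation between events, no reduction at the first Grade 2 event, and a one-level reduction at the second.

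| Dose at 1st event | Grade 3 reading | Grade 2 reading |
|---|---|---|
| 160 mg | 120, 80, stop at 3rd | 160, 120, 80, stop at 4th |
| 120 mg | 80, below 80 at 2nd | 120, 80, below 80 at 3rd |
| 80 mg | below 80 at 1st | 80, below 80 at 2nd |

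The readings differ by one event. The difference can vanish: footnote d takes patients needing more than 2 reductions off protocol therapy. If the optional first reduction is made and each later event adds a level, the Grade 2 path reaches 1 + 1 + 1 = 3 reductions at the 3rd event, the same event at which the Grade 3 path stops.

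**The case against.** The strongest reply is that the documents already point to the CTCAE row. The further-description row is labelled as examples, Table 8.22b is keyed to the CTCAE v5.0 grade, Section 10.1 makes CTCAE the adverse-event scale, and the activities row agrees with the CTCAE row in the case above. This stands as far as it goes: it makes the CTCAE row the likelier reading. But Section 8.22 refers sites to the whole table, the conflicting row is part of it, and no sentence ranks the rows.

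A second reply is that Table 8.22b offers suggested modifications, Section 8.22 is permissive, and footnote a allows more conservative management. This softens the contrast, because a site may interrupt and reduce for a Grade 2 event. It does not settle the grade or the occurrence count. Footnote a also works in one direction only: it does not allow a Grade 3 event to be handled less conservatively.

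A reader might also infer that the CTCAE row puts all painful blistering in Grade 2, or that the two grades lead to different handling throughout. Neither is supported. The CTCAE row lists blisters under Grade 3 when the changes are severe, and from the 2nd Grade 2 occurrence, or on failure to improve, therapy is interrupted and the dose reduced as well.

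**Conclusion.** The conflict is real but narrow. It concerns painful, non-severe blistering that limits only instrumental activities. It matters mainly at the first event, most of all at 80 mg, where one reading ends regorafenib. A secondary effect is a difference of at most one event in the count to stopping, under the assumptions in Step 4. What is at risk is consistent dosing across sites, and agreement between the grade used for dosing and the grade on the adverse-event form.

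A reader might infer a measurable shift in the reported Grade 3 rate, starting from the 16.6% in Section 1.5. The documents do not support one. They give neither the Grade 2 rate nor the share of reactions that blister. The 16.6% comes from an earlier placebo-controlled regorafenib trial, and Section 1.4 describes standard dosing as 160 mg daily, whereas this trial starts at 80 mg and escalates. Arm B patients receive regorafenib only if re-registered, so the number exposed in that arm is unknown. If forms are completed by CTCAE as Section 16.326 intends, the reported rate need not move at all.

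Nor does the point reach the main inference. The primary test compares overall survival by randomised arm, the sample size does not use toxicity grades, and the stopping rule in Section 16.42 counts grade 4 and above, while Table 8.22a ends at Grade 3.

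**What to change.** Reconcile the rows of Table 8.22a so that painful, non-severe blistering falls in one grade, or add a sentence naming the row that governs when they disagree. State that the same grade is used for Table 8.22b and for adverse-event reporting. When this is done, check the first-event Grade 3 rule against Section 8.12 at 80 mg, so that the result there is intended. Which grade and which action apply is for the sponsor to decide. The cost is an edit to one table and a sentence or two of text; no new data, design change or recalculation is needed.

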8.23 Hypertension

Hypertension is a known AE associated with regorafenib treatment. Subject will have their blood pressure measured at least weekly during the first 5 weeks of treatment. If additional blood pressure measurements are done outside the study site, and the blood pressure is >140 mm Hg systolic or >90 mm Hg diastolic (NCI CTCAE v5.0), then the subject must contact

study personnel. The management of hypertension, including the choice of antihypertensive medication, will be performed according to local standards and to the usual practice of the treating physician. Every effort should be made to control blood pressure by medical means other than study drug dose modification. If necessary, Tables Section 8.1 and 8.2 outline suggested dose reductions.

Table 8.23: Management of Treatment-Emergent Hypertension

Grade (CTCAE v5.0)	Antihypertensive Therapy	Regorafenib Dosing
1 Prehypertension (systolic BP 120 - 139 mmHg or diastolic BP 80 - 89 mmHg)	None	Continue regorafenib Consider increasing blood pressure (BP) monitoring
2 Systolic BP 140 - 159 mmHg or diastolic BP 90 - 99 mmHg, OR Symptomatic increase by >20 mmHg (diastolic) if previously within normal limits	Treat with the aim to achieve diastolic BP \leq 90 mm Hg: If BP previously within normal limits, start anti-hypertensive monotherapy If patient already on anti-hypertensive medication, titrate up the dose.	Continue regorafenib If symptomatic, hold regorafenib until symptoms resolve AND diastolic BP \leq 90 mm Hg ^a . When regorafenib is restarted, continue at the same dose level.
3 Systolic BP \geq 160 mmHg or diastolic BP \geq 100 mmHg OR More than one drug or more intensive therapy than previously used indicated	Treat with the aim to achieve diastolic BP \leq 90 mm Hg: Start anti-hypertensive medication AND/OR Increase current anti-hypertensive medication AND/OR Add additional anti-hypertensive medications.	Hold regorafenib until diastolic BP \leq 90 mm Hg, and if symptomatic, until symptoms resolve ^a When regorafenib is restarted, continue at the same dose level. If BP is not controlled with the addition of new or more intensive therapy, reduce by 1 dose level. If Grade 3 hypertension recurs despite dose reduction and antihypertensive therapy, reduce another dose level.
4 Life-threatening consequences (e.g., malignant hypertension, transient or permanent neurologic deficit, hypertensive crisis)	Per institutional guidelines	Discontinue therapy

a. Patients requiring a delay of >4 weeks should go off protocol therapy If BP remains controlled for at least one cycle. Patients requiring >2 dose reductions should go off protocol therapy.
 
b. If BP remains controlled for at least one cycle, dose re-escalation permitted per treating physician's discretion.
 
c. Patients requiring >2 dose reductions should go off protocol therapy.
		

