10.5 Other Required Reporting

10.5.1 Unanticipated Problems Involving Risks to Subjects or Others (UPIRTSOS) in general, include any incident, experience, or outcome that meets all of the following criteria:

1. Unexpected (in terms of nature, severity, or frequency) given (a) the research procedures that are described in the protocol-related documents, such as the IRB-approved research protocol and informed consent document; and (b) the characteristics of the subject population being studied;
2. Related or possibly related to participation in the research (in this guidance document, possibly related means there is a reasonable possibility that the incident, experience, or outcome may have been caused by the procedures involved in the research); and
3. Suggests that the research places subjects or others at a greater risk of harm (including physical, psychological, economic, or social harm) than was previously known or recognized.

Some unanticipated problems involve social or economic harm instead of the physical or psychological harm associated with adverse events. In other cases, unanticipated problems place subjects or others at increased *risk* of harm, but no harm occurs.

Note: If there is no language in the protocol indicating that pregnancy is not considered an adverse experience for this trial, and if the consent form does not indicate that subjects should not get pregnant/impregnate others, then any

pregnancy in a subject/patient or a male patient's partner (spontaneously reported) which occurs during the study or within 120 days of completing the study should be reported as a UPIRTSO.

If the event meets the criteria for an UPIRTSO, submit to your IRB as required by your institutional policies.

10.52 Adverse events to be graded at each evaluation and pretreatment symptoms/conditions to be evaluated at baseline per the CTCAE v5.0 grading unless otherwise stated in the table below:

System Organ Class (SOC)	Adverse event/Symptoms	Baseline	Each evaluation
Gastrointestinal disorders	Diarrhea	# stools per day	X
	Nausea	X	X
	Vomiting	X	X
General Disorders	Fatigue	X	X
	Palmar-plantar erythrodysesthesia syndrome	X	X
Skin and Subcutaneous Tissue Disorders	Rash maculo-papular	X	X
Vascular disorders	Hypertension	X	X
Investigations	Blood bilirubin increased	X	X
	Alanine aminotransferase increased	X	X
	Aspartate aminotransferase increased	X	X

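### Table 8.23 tells sites both to continue and to hold regorafenib in an asymptomatic patient on antihypertensive treatment whose diastolic pressure is above 90 and below 100 mmHg and systolic pressure below 160 mmHg

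*Combined protocol and SAP*

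**What the plan says.** All the key text is in Table 8.23 (section 8.23).

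- **Grade 2, definition:** "Systolic BP 140 - 159 mmHg or diastolic BP 90 - 99 mmHg", with a symptomatic diastolic rise of more than 20 mmHg as an alternative.
- **Grade 2, blood-pressure treatment:** a previously normotensive patient starts one drug. For the others: "If patient already on anti-hypertensive medication, titrate up the dose".
- **Grade 2, regorafenib:** "Continue regorafenib If symptomatic, hold regorafenib until symptoms resolve AND diastolic BP" is 90 mmHg or below.
- **Grade 3, definition:** systolic pressure of 160 mmHg or more, or diastolic pressure of 100 mmHg or more, OR "More than one drug or more intensive therapy than previously used indicated".
- **Grade 3, blood-pressure treatment:** the options include "Increase current anti-hypertensive medication".
- **Grade 3, regorafenib:** "Hold regorafenib until diastolic BP" is 90 mmHg or below, whether or not there are symptoms. Restart is at the same dose level. One level is lost if pressure is not controlled on the stronger therapy, and another if Grade 3 recurs.

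The text above the table adds: "Every effort should be made to control blood pressure by medical means other than study drug dose modification". Section 8.0 requires the modification tables to be followed strictly for the first two cycles and treats them as guidelines after that.

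**The concern.** The act that the Grade 2 row orders for a patient already on treatment is enough, by itself, to satisfy the Grade 3 row. Where the two rows then differ on regorafenib, a site cannot obey both.

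The patients exist in this trial. Exclusion 3.26 removes only hypertension that is uncontrolled despite optimal medical management, so treated and controlled patients may enter. A patient started on one drug under the Grade 2 row also becomes a treated patient at the next raised reading. Both arms are planned to receive regorafenib, Arm A first and Arm B second (section 7.0). Section 8.23 asks for pressure at least weekly during the first five weeks, which lies inside the two-cycle window in which the tables bind.

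At stake is whether study drug is interrupted. One site may continue regorafenib and another may hold it at the same pressure. Only the Grade 3 row can lead on to dose reduction.

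**Working it through.** No stated figure has to be reproduced. The check is to run test pressures through the two rows for a patient already on an antihypertensive drug.

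**Step 1: can the Grade 3 row be met at Grade 2 pressures?** Its pressure criterion and its therapy criterion are joined by OR, so either is sufficient. The Grade 2 row orders the current dose raised. A raised dose is more intensive than the therapy used before, and the table itself indicates it. The Grade 3 treatment column lists the same act. So the therapy criterion is met.

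**Step 2: where do the regorafenib orders differ?**

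| Case (already treated) | Grade 2 row | Grade 3 row | Result |
|---|---|---|---|
| 150/95, no symptoms | Raise dose, continue regorafenib | Met by therapy criterion; hold, since 95 > 90 | Direct conflict |
| 150/95, symptoms | Hold until symptoms resolve and diastolic ≤ 90; same dose on restart | Hold on the same terms; same dose on restart | No dosing conflict; grade unclear |
| 150/85, no symptoms | Raise dose, continue regorafenib | Met by therapy criterion; the hold ends at diastolic ≤ 90 and 85 already satisfies that | Little dosing effect; grade unclear |
| 165/95 or 150/102 | Not needed | Met on pressure alone; hold if diastolic > 90 | No conflict from the therapy criterion |

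**Step 3: the range in which the conflict is live.** Four conditions are needed together: already on treatment; no symptoms; diastolic pressure above 90 (otherwise the Grade 3 hold has nothing to wait for); and diastolic below 100 with systolic below 160 (otherwise Grade 3 is reached on pressure). The uncertainty about the grade label is wider and covers the whole treated Grade 2 band.

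**Step 4: does any other text settle it?**

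- The footnotes to Table 8.23 deal with length of delay, re-escalation and number of reductions, not with choice of row.
- The tie-break in section 8.0 takes the greatest reduction when several adverse events occur together. Here there is one event that fits two rows, and the question is a hold, not a reduction.
- The preference for medical control in section 8.23 is about dose modification. Section 7.0 defines modification as a change of dose level and defines delay separately, so that sentence does not decide whether to hold.
- A rule that the highest grade met applies is stated nowhere. It would leave the Grade 2 instruction to raise the dose with no patient to apply to.

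**The case against.** The best reply is that the table has a coherent reading. The Grade 2 row addresses exactly this patient and says what to do, so the specific instruction governs its pressure band and the Grade 3 therapy criterion is kept for other cases. The surrounding text leans the same way: management follows local standards and usual practice, medical control is preferred, and the dose reductions are called suggested. On that view a site query would settle the matter. The reading is plausible, but it is not written down. Section 8.0 makes the tables strict in just the period when pressure is checked weekly, so the contradiction stands as text.

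The reply does succeed against several stronger inferences that a reader might draw.

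- *Every treated patient in the Grade 2 band gets conflicting orders.* Not so: symptomatic patients are held under both rows, and at diastolic 90 or below the Grade 3 hold has already lapsed.
- *The Grade 3 row leads to the exit for more than two reductions.* It provides for at most two. From 160 mg that gives 160 − 40 − 40 = 80 mg, the lowest level in section 8.1. A patient starting from a lower level could fall under the separate rule in 8.12, but only after pressure stays uncontrolled following restart at the same dose.
- *The severity summary is corrupted.* Sections 10.1, 10.52 and 16.326 all name CTCAE v5.0 as the grading source, and Table 8.23 is a management table. Its grade column carries the same CTCAE label, so the label is ambiguous for treated patients, but a distorted adverse-event rate is not shown.

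**Conclusion.** Table 8.23 is wrong as written: it contradicts itself for an asymptomatic patient already on antihypertensive medication with diastolic pressure above 90 and below 100 mmHg and systolic pressure below 160 mmHg. The direct consequence is that regorafenib may be held at some sites and continued at others. Dose reduction may follow under the Grade 3 row if pressure stays uncontrolled.

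The size cannot be given. A reader might assume that 30–60% of patients enter on antihypertensives and that 20–40% of those reach the Grade 2 band, which yields 0.3 × 0.2 = 6% to 0.6 × 0.4 = 24%. The documents contain neither share. The product also counts symptomatic patients and those with diastolic pressure of 90 or below, who have no effective dosing conflict. The 7.2% rate of grade 3 or higher hypertension in section 1.5 comes from the earlier placebo-controlled phase III trial of regorafenib and does not measure this group.

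A reader might also infer harm to the primary comparison. Nothing in the documents shows an effect on the overall survival test, and the stopping rule in 16.42 counts grade 4 or higher events, so a choice between Grade 2 and Grade 3 does not enter it.

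The conclusion rests on two readings: that OR makes each Grade 3 criterion sufficient, and that a raised dose counts as more intensive therapy. Severity is minor.

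**What to change.** Reconcile the Grade 2 and Grade 3 rows of Table 8.23 so that a patient already on antihypertensive treatment, with pressure in the Grade 2 band, falls in one row only and has one regorafenib instruction. Which row governs is the sponsor's clinical decision, and this review takes no view on it. Once the rows are separated, the grade label for treated patients in that band is settled within the table as well.

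The cost is one wording change in the table, passed on to sites. It needs no new visits, no new data and no change to the sample size or analysis.
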